#### **7.1.4.2. Data Analytic Models**

All primary endpoint efficacy measurements available at post-baseline at scheduled measurements (Visits 2 through 5 [infusions 1 through 4] for inflammatory markers, oxygenation, and room air status) will be analysed in a generalized linear mixed model. The model will predict each outcome as a function of the interaction between the fixed factors treatment group and time, controlling for lower order effects of time and treatment group. Models will control for stratification variables (see [Covariates and Other Strata](#)), and subject will be included as random effects.

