## 5.3. Baseline Definitions

For all endpoints, the baseline value will be the latest pre-treatment assessment visit with a non-missing value. i.e., If an assessment has been made both at screening visit (Visit 1), and Day 0, infusion 1 visit (Visit 2, Day 0), the value from the Day 0 visit is used as the baseline value. If the value measured at the Day 0 visit is missing and the assessment also has been made at screening, then the screening value is used as the baseline value.

Unless otherwise stated, if baseline data is missing, no derivation will be performed and baseline will be set to “missing”.

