### 5.3.1. Change from Baseline

Definition	Reporting Details
Change from Baseline	= Post-Dose Visit Value – Baseline
% Change from Baseline	= $100 \times [(Post-Dose Visit Value – Baseline) / Baseline]$

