## **5.4. Examination of Covariates, Other Strata and Subgroups**

### **5.4.1. Covariates and Other Strata**

Baseline will be included as a covariate in the efficacy analyses, wherever applicable. Stratification variables used at randomization (site, illness severity, pre-existing condition, ethnicity, age group) will be included as covariates.

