The Bayesian approach addresses these questions: (1) “Among patients with suspected COVID-19, what is the probability that allogeneic HB-adMSC 100mm confers benefit relative to placebo on status on inflammatory markers (C-Reactive protein, TNF-alpha, IL-6, IL-10), change from baseline oxygenation, and time to return to room air (RTRA) at treatment Day 10?” (2) “What is the best estimate of these effects?” and (3) “What is their precision?” By estimating the probability that such effects exist, we are assessing the probability that the alternative hypothesis is true; a probability that is, by definition, not accessible to Frequentist methods. The FDA has discussed the use of Bayesian statistical methods to make decisions regarding the efficacy of new treatments as an alternative to Frequentist methods in developing clinical applications. The current proposal will provide the optimal, unbiased estimates for the benefit conferred by allogeneic HB-adMSC, while also estimating the probability that such effects exist. Posterior distributions can then be used as informative priors for continued monitoring in expansions of treatments and treatment strategies exhibiting initial promise.

Presentation of results from the statistical models will include the estimated conditional/marginal mean treatment effects. For all endpoints analysed statistically, estimated mean treatment differences will be presented together with 95% credible intervals and posterior probabilities,

HB-adMSCs 100MM vs Placebo

All safety evaluations will be presented using Safety Analysis Set. The efficacy analysis will be presented using Efficacy analysis set.

Individual safety and efficacy parameters will be listed.

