## 7. EFFICACY ANALYSES

### 7.1. Primary Efficacy Analyses

#### 7.1.1. Endpoint / Variables

The primary efficacy endpoints are changes from baseline in the following outcomes at each post-baseline visit:

- Inflammatory markers (TNF-alpha, IL-10, IL-6, C-Reactive protein)
- Oxygenation
- Time to return to room air (RTRA) and proportion of patients with room air status

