#### 7.1.2. Summary Measure

Mean values (descriptive, unadjusted for covariates) and conditional means from the Bayesian generalized linear (mixed) models (estimated, adjusted for covariates) will be provided for each endpoint.

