Evaluation of posterior distributions will permit statements regarding the probability that effects of varying magnitudes exist, given the data. Specification of diffuse, neutral priors will reflect the initial uncertainty regarding effect sizes. For all generalized linear models, priors for regression coefficients will be specified as  $\sim$ Normal ( $\mu=0$ ,  $\sigma^2=1 \times 10$ ), and priors for the levels one and two error variances will be specified as  $\sim$ Half-Normal ( $\mu=0$ ,  $\sigma^2=1 \times 10^3$ ). The choice of prior distribution for level two variances will follow Gelman's recommendations from the literature. Priors for the comparison of proportions will be specified as  $\sim$ Beta ( $\alpha=1.0$ ,  $\beta=1.0$ ).

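### SAP 7.1.4.2 and 7.2.4.2 model Visit 2 (Day 0), the baseline, as a post-baseline response; with change scores, or a baseline covariate and stable variance, the Day 10 interval is too narrow where the prior is diffuse

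*SAP*

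**What the plan says.** SAP 5.3 takes the latest pre-treatment assessment as baseline; where screening and Day 0 values both exist, "the value from the Day 0 visit is used as the baseline value". Day 0 is Visit 2 in protocol Table 2, where the inflammatory and exploratory marker rows begin at that visit. SAP 5.3.1 defines change as "Post-Dose Visit Value – Baseline", and SAP 7.1.1 states: "The primary efficacy endpoints are changes from baseline in the following outcomes at each post-baseline visit".

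SAP 7.1.4.2 then puts into the mixed model "All primary endpoint efficacy measurements available at post-baseline at scheduled measurements (Visits 2 through 5 [infusions 1 through 4] for inflammatory markers", with oxygenation and room-air status alongside. SAP 7.2.4.2 uses the same starting visit for exploratory markers and clinical laboratories, and Visits 2 to 6 for chest X-ray, CT and the ordinal scale. SAP 7.2.1 says the imaging changes exist at Visit 6 alone.

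The model has treatment, time and their interaction, the stratification variables and a subject random effect. SAP 5.4.1 adds: "Baseline will be included as a covariate in the efficacy analyses, wherever applicable". On priors, SAP 7.1.4.1 says "For all generalized linear models, priors for regression coefficients will be specified as" Normal with mean 0 and a variance printed as 1 × 10. It describes level-one and level-two error variances and nothing that lets the residual variance differ by visit. For reporting, SAP 7.1.2 says "conditional means from the Bayesian generalized linear (mixed) models (estimated, adjusted for covariates) will be provided for each endpoint", and SAP 5.7 says "estimated mean treatment differences will be presented together with 95% credible intervals and posterior probabilities", with its efficacy question put at Day 10.

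**The concern.** One measurement cannot be both the baseline and a follow-up response without consequences for the model. If the response is the change score, Visit 2 adds a column of zeros. If the Day 0 value is also a covariate, Visit 2 adds rows that the covariate largely explains. Either way a single residual variance is pulled down by rows that say nothing about variability after treatment, and the same variance sets the width of the Day 10 interval.

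At stake are the Day 10 mean differences, credible intervals and posterior probabilities for the primary markers, which could look more certain than they are. The SAP does not say whether raw values or changes are modelled, or whether baseline is a covariate here, so the visit list alone does not tell the analyst which model to fit.

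**Working it through.** The plan has no figure of its own to reproduce: the protocol bases the sample size on anticipated demand and gives no SD, effect size or power. The benchmark is the nominal 95% level.

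**Inputs from the documents:** 60 and 40 patients per arm; Visits 2–5 = Days 0, 3, 7, 10; treatment by categorical time; subject random effect, read as an intercept; one residual variance.

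**Assumptions:** complete data; equal outcome variance at each visit (SD 1); equal within-patient correlation r of 0.3, 0.5 or 0.7; diffuse prior. The arm-size factor is √(1/60 + 1/40) = 0.2041.

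**Reading 1: change scores, no baseline covariate.** Each post-baseline change has variance v = 2(1 − r). The visit variances are (0, v, v, v), which the model averages to 0.75v. The SE ratio is √0.75 = 0.866 for any r. Coverage is 2Φ(1.96 × 0.866) − 1 = 91.0%. At r = 0.5, v = 1: the half-width is 1.96 × 0.2041 × 0.866 = 0.346, where 0.400 is needed.

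**Reading 2: Day 0 as covariate with one slope, raw or change response (same fit).** For raw responses the fitted slope is b = (1 + 3r)/4. Residual variance is (1 − b)² at Visit 2 and 1 − 2br + b² at later visits. At r = 0.5: b = 0.625, variances 0.1406 and 0.7656, average (0.1406 + 3 × 0.7656)/4 = 0.6094, ratio √(0.6094/0.7656) = 0.892. At r = 0.3 and 0.7 the ratios are 0.907 and 0.880. Coverage is 92.5/92.0/91.5%.

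**Reading 3: raw values, Day 0 a response, no covariate.** The Day 10 SE is 0.2041, correctly estimated. Baseline adjustment would give 0.2041 × √(1 − r²) = 0.177 at r = 0.5 and 0.146 at r = 0.7.

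**Simulation** (10,000 trials per setting, SD 1, printed coefficient prior, no true effect):

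| Model | Coverage at r = 0.3/0.5/0.7 |
|---|---|
| Reading 1 | 90.6/91.0/90.8% |
| Reading 2 | 92.7/92.1/91.4% |
| Reading 3 | 94.5–95.0% across the three |
| Visits 3–5, baseline-by-visit | 95.2/95.2/94.9% |

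At r = 0.5, model SE against empirical SD is 0.176 vs 0.203 (reading 1), 0.159 vs 0.178 (reading 2) and 0.177 vs 0.178 (Visits 3–5). With 51/34 patients (15% lost), readings 1 and 2 cover 90.6/90.0/90.2% and 92.2/91.8/91.3%. Taking a posterior probability of benefit above 95% as an example threshold (the SAP sets none), it is passed with no true effect in 7.9–8.2% of trials (reading 1) and 6.7–7.6% (reading 2), against 5.0–5.2% with Visits 3–5. With a 0.5 SD effect, reading 3 passes it in 79/79/79% of trials, against 82/88/96% for the adjusted difference.

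**Treatment-by-time contrast at Day 10.** Coverage is 94.8–95.2%, but its variance is 2/(1 + r) times that of the adjusted difference: 1.54/1.33/1.18.

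**Unequal variance.** When variance falls to half by Day 10, reading 2 covers 95.7/94.6/94.1%; when it falls to a quarter, 98.1/97.3/97.8%. Reading 1 stayed below nominal in every pattern tried.

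**Prior scale.** For a single coefficient at SD 1, the likelihood variance is 0.2041² = 0.0417, and a prior variance of 10 changes the SE by 0.2%. At SD 20 it multiplies the SE by 0.61, so shrinkage dominates. If the printed 1 × 10 has lost an exponent and 10³ was meant, SD 10 behaves as SD 1 does here.

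**The case against.** The strongest defence is that SAP 7.1.4.2 speaks of measurements and outcomes and centres on treatment-by-time, so raw values with Day 0 as the first response (reading 3) may be what was meant. The imaging wording supports this, since a treatment-by-time model for X-ray and CT makes sense only if the Day 0 image is a response. On that reading the mean difference and the interaction are both calibrated under equal variances and correlations. SAP 5.4.1 also allows the covariate to be left out where it does not apply. A column of zero changes, moreover, sits badly with SAP 5.3.1 and 7.1.1, which confine change to post-dose, post-baseline visits.

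This stands as far as it goes: under-coverage is possible, not established. It does not clear the text. The endpoint is defined as a change, 7.1.4.2 points to the section that adds the baseline covariate, and Visit 2 is called post-baseline. The raw reading also gives up precision.

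Other limits stand too. The SDs and correlations are assumed, and the simulation leaves out site and stratification terms. Removing Visit 2 is not a complete cure: under serial correlation with adjacent-visit correlation 0.3/0.5/0.7, Visits 3–5 with baseline-by-visit covers 94.4/92.5/91.7%, and with rising variance about 92%.

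A reader might also infer that the laboratory baseline is unsettled, because the protocol's screening text says screening samples set it, or that the Day 0 oxygenation baseline is unclear, because vital signs are read during the infusion. SAP 5.3 answers both by taking the latest pre-treatment value.

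**Conclusion.** The visit list is wrong as written: SAP 7.1.4.2 and 7.2.4.2 call the baseline visit post-baseline. For continuous outcomes with a random intercept, one residual variance and a diffuse prior:

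- Change scores without a covariate give a Day 10 SE 0.866 of what it should be and coverage of about 91%, given equal post-baseline change variances.
- With the baseline covariate, coverage is about 91.5–92.5% under stable variance and equal correlations. If variance falls to half or less by Day 10 under equal correlations, coverage is roughly nominal or above.
- Raw values without a covariate are calibrated under equal variances and correlations but less precise (SE about 0.20, against 0.18 at r = 0.5 and 0.15 at r = 0.7).

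A reader might infer that the planned primary intervals are too narrow whichever model is fitted. The documents do not support that: they permit the raw-value reading, and they give no variances. Results at outcome SD 5–20 depend on the printed prior variance, which needs confirming. Room-air status, the ordinal scale, time-to-event and adverse-event outcomes were not quantified. Confidence is high for the visit conflict and moderate for the size of the interval error.

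**What to change.** For continuous outcomes with repeated follow-up, list Visits 3–5 (and Visit 6 where measured) as the responses, and use the Day 0 value only as a baseline covariate whose effect may vary by visit. State whether raw values or changes are modelled, and on what scale (original, log or standardised), so that the stated prior is diffuse on it; confirm the 1 × 10 variance. Let residual variance and correlation differ by visit, because dropping Visit 2 alone does not protect against serial correlation or rising variance. Report the adjusted Day 10 difference, which answers the question in SAP 5.7.

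Analyse chest X-ray and CT as one baseline-adjusted follow-up comparison, and reconcile SAP 7.2.4.2 (Visits 2–6) with 7.2.1 (Visit 6 only). Add a sentence each on how Visit 2 is handled for room-air status and the ordinal scale.

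The cost is a few lines in a SAP still marked as a draft, and a few more model parameters. A patient with no Day 0 marker value would stay in through the joint missing-data model the SAP already plans. There is no data or patient cost.

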## 7.2. Secondary Efficacy Analyses

### 7.2.1. Endpoints / Variables

Change from baseline through Visit 5 (Day 10):

- Change in clinical laboratories
- Change from baseline in exploratory markers (D-dimer, myoglobin, troponin, creatinine kinase, serum ferritin, CD3CD56, CD4/CD8, VEGF)

Change from baseline through Visit 6 (Day 28):

- Change from baseline Chest X-ray (available at Visit 6 only)
- Change from baseline CT scan (available at Visit 6 only)
- Time to negative PCR test results
- Change from baseline in the 7-point ordinal scale

Cumulative:

- Cumulative incidence of serious adverse events (SAEs) or adverse events (AEs)

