Patients will be considered to have completed the study if they complete treatment and assessments through day 28. A patient's investigational treatment should be discontinued if any of the following situations occurs:

- The Investigator believes that for safety reasons, it is in the best interest of the patient to stop treatment.
- The patient is non-compliant with the study visit schedule or other protocol requirements.
- The patient develops a severe allergic reaction that occurs following investigational product administration.

A patient may voluntarily withdraw or be withdrawn from the study at any time for reasons including, but not limited to, the following:

- Patient withdrawal of consent: At any time, a patient's participation in the study may terminate at his/her request. The specific reason for patient withdrawal will be noted on the case report form (CRF).
- Lost to follow-up: The patient stops coming for visits, and study personnel is unable to contact the patient after repeated attempts (e.g., mail, or email).
- This study may be terminated at the discretion of the Sponsor or any regulatory agency.

If a patient's infusions are discontinued at any point during the trial and the patient maintains consent to contribute additional outcome information, the patient should continue to be followed through day 28 for all safety and efficacy assessments. Investigators will be trained about the importance of retention and steps to prevent missing data. The date and reason for withdrawal are to be documented in the CRF. The study site(s) must immediately notify the medical monitor. The patients who withdraw prematurely must attend an early discontinuation visit if possible, at which time they will complete all assessments described in Table 2 under day 28. Unless the patient declines (consent withdrawn), the follow up phone call at day 28 should be done in all patients who were enrolled in the study regardless of their enrollment status.

In the event that a patient discontinues prematurely from the study due to an Adverse Event (AE) or serious AE, the event will be followed until it resolves (returns to normal or baseline values) or stabilizes, or until it is judged by the Investigator to be no longer clinically significant. Once a patient is withdrawn from the study, the patient may not re-enter the study.

Treatments

Details of the investigational product

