All medications, including over-the-counter treatments and preventative vaccines taken by the patient during the study, including those treatments initiated prior to the start of the study, must be recorded in the CRF. The entry must include the dose, regimen, route, indication, and dates of use.

Study Procedures

Table 2 outlines the timing of procedures, and assessments to be performed throughout the study.

Table 2. Schedule of Assessments

Visit Number	1	2	3	4	5	6
Days	N/A	Day 0	Day 3	Day 7	Day 10	Day 28
Visit Name	Screening	Baseline/ Infusion 1	Infusion 2	Infusion 3	Infusion 4	End of Study / Telephone Encounter**
Window Period	Up to 7 days	±3 days	±3 days	±3 days	±3 days	±3 days
STUDY PROCEDURES						
Informed Consent	X					
Demographics	X					
Inclusion and Exclusion Criteria	X					
Medical History Review	X	X	X	X	X	X
Concomitant Medication Review	X	X	X	X	X	X
Eligibility	X					
Randomization	X					
Adverse Event Monitoring		X	X	X	X	X
ASSESSMENTS						
Vital Signs	X	X	X	X	X	
Weight and Height ¹	X	X	X	X	X	
Physical Examination	X	X	X	X	X	
Ordinal Scale		X	X	X	X	X
CBC with differential	X	X	X	X	X	
Comprehensive Metabolic Panel	X	X	X	X	X	
Coagulation Panel	X	X	X	X	X	
Urinalysis with pregnancy test (childbearing age women only)	X					
PCR test for SARS-CoV-2		X	X	X	X	
Exploratory Laboratory Assessments ²		X	X	X	X	
Inflammatory Marker Laboratory Assessments ³		X	X	X	X	
EKG		X*	X*	X*	X*	
CT Scan		X				X
Chest X Ray (PA, Single View) ⁴		X				X
ADMINISTRATION						
Allogeneic HB-adMSCs Administration		X	X	X	X	

1. Height will only be measured at screening

2. Exploratory laboratory Assessments: Natural Killer Cell Surface Antigen (CD3-CD56+ Marker Analysis), Troponin, Myoglobin, Creatine Kinase (CK) MB, Serum ferritin, CD4+/CD8+ ratio, D-dimer

3. Inflammatory Marker Laboratory assessments: CRP, IL-6, IL-10, TNFa

4. Chest Xray and CT scan will be performed as scheduled, however, if the patient is discharged prior to the scheduled tests at 28 days, any imaging (CT/Xray) done at discharge

* Subsequent EKG will be performed if necessary, such as abnormal result at baseline

** Telephone encounter is conducted if subject has been discharged

Informed Consent (ICF)

Prior to commencement of any trial related activity, the investigator or designated staff will obtain written informed consent from the patient or their Legally Authorized Representative (LAR).

Patient Re-Screening

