- Medical History will be reviewed and updated if necessary. This includes recording results of COVID-19 testing. If the patient reported a medication which does not match the current medical history, further investigation will be required to determine whether it was an Adverse Event, or the patient just forgot to mention it before. If it is found to be an AE, it should be recorded in the appropriate CRF. If the patient forgot to mention it before, a note to file (NTF) should be made to clarify the case.
- A PCR analysis to detect SARS-CoV-2 virus will be performed with a nasal swab
- Blood samples will be collected for laboratory assessments.
- Ordinal Scale to be performed.
- Administer investigational product.
- Monitor for AEs. Observe the patient for at least 1 hour after infusion for symptoms of infusion-related reactions and allergic reactions, including anaphylaxis (See Appendix 1).
- Instruct the patient on recognition of delayed serious allergic reactions, including anaphylaxis and seeking for medical assistance.
- Chest X-ray will be performed or collected from hospitalization due to COVID-19.
- CT scan will be performed or collected from hospitalization due to COVID-19.

Infusion # 2 (Day 3) and #3 (Day 7) and #4 (Day 10)

- Weight will be measured
- Vital Signs will be measured.
- Concomitant medications will be reviewed and updated if necessary.
- Medical History will be reviewed and updated if necessary. This includes recording results of COVID-19 testing. If the patient reported a medication which does not match the current medical history, further investigation will be required to determine whether it was an Adverse Event, or the patient just forgot to mention it before. If it is found to be an AE, it should be recorded in the appropriate CRF. If the patient forgot to mention it before, a note to file (NTF) should be made to clarify the case.
- A PCR analysis to detect SARS-CoV-2 virus will be performed with a nasal swab
- Blood samples will be collected for laboratory assessments.
- Ordinal Scale to be performed.
- Administer investigational product.
- Monitor for AEs. Observe the patient for at least 1 hour after infusion for symptoms of infusion-related reactions and allergic reactions, including anaphylaxis (See Appendix 1).
- Instruct the patient on recognition of delayed serious allergic reactions, including anaphylaxis and seeking for medical assistance.

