- Chest X-ray will be performed at discharge or 28 days, whichever occurs first

- CT scan will be performed at discharge or 28 days, whichever occurs first

Follow Up “Day 28” (EOS)

- Follow up phone call.
If a patient prematurely withdraws from the study for any reason, the early discontinuation visit requirements should be completed. If the early discontinuation visit is not done, the reason(s) will be recorded in the CRF.
- Ordinal Scale to be performed based upon information obtained during follow up phone call.

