The primary role of TNF is in the regulation of immune cells. TNF, being an endogenous pyrogen, is able to induce fever, apoptotic cell death, cachexia, inflammation and to inhibit tumorigenesis and viral replication and respond to sepsis via IL1- & IL6-producing cells.

IL-6

Interleukin 6 (IL-6) is an interleukin that acts as both a pro-inflammatory cytokine and an anti-inflammatory cytokine. In humans, it is encoded by the *IL6* gene.

IL-10

IL-10 is a cytokine with multiple effects in immunoregulation and inflammation. It downregulates the expression of Th1 cytokines, MHC class II antigens, and co-stimulatory molecules on macrophages. It also enhances B cell survival, proliferation, and antibody production.

VEGF

VEGF is vascular endothelial growth factor. It is a signal protein produced by cells to stimulate angiogenesis. Increased levels of VEGF in the blood can indicate increased inflammation.

D-dimer

D-dimer is a protein fragment produced by dissolution of blood clots. Levels detectable in blood indicate clot formation and degradation within the system.

Myoglobin

A cytoplasmic protein that binds oxygen on a heme group. Functions to store oxygen. Increased myoglobin occurs when muscle tissue is damaged.

Troponin

A regulatory protein involved in muscle contraction. Can be used to indicate damage to myocardium. Increased troponin indicates recent cardiac muscle damage.

Creatinine Kinase

An enzyme involved in conversion of creatine in tissues that rapidly consume ATP, such as muscle. Higher levels of creatinine kinase are measured in the blood to identify damage to these tissues, such as myocardial infarction.

Serum Ferritin

An intracellular protein involved in iron storage. This test is generally used as a diagnostic for iron-deficiency anemia. High levels of serum ferritin may also indicate an acute inflammatory reaction, such as infection.

PCR nasopharyngeal swab

To detect viral target for Human Coronavirus (SARS-CoV-2), which would indicate active infection. If a subject with a previous positive PCR result obtains two negative PCR results consecutively, they are considered clear of active infection.

Safety Assessments

Safety assessments (vital signs, weight, physical examinations, EKG recordings, AEs, routine clinical laboratory tests (CBC, CMP, PT, PTT/INR and urinalysis) and chest x-rays will be performed at the visits specified in the schedule of assessments in Table 2.

Vital Signs, Height, and Weight

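### Time to negative PCR is placed on a Day 28 horizon, but no PCR is scheduled after Visit 5 (Day 10) and the analysis set includes patients who may never test positive

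*SAP*

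**What the plan says.** **Horizon.** SAP 7.2.1 puts "Time to negative PCR test results" in the list whose heading begins "Change from baseline through Visit 6 (Day 28". Clinical laboratories and exploratory markers, which are last drawn at Visit 5, stand in the separate list that ends at Visit 5 (Day 10).

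**Swab schedule.** The row "PCR test for SARS-CoV-2" in protocol Table 2 is marked at Visits 2 to 5 only. The visit text agrees. For Infusion 1 and again for Infusions 2 to 4 it states "A PCR analysis to detect SARS-CoV-2 virus will be performed with a nasal swab". For Day 28 it lists a phone call and "Ordinal Scale to be performed based upon information obtained during follow up phone call", with no swab. The Table 2 footnote adds "Telephone encounter is conducted if subject has been discharged". Patients who withdraw early are asked to "complete all assessments described in Table 2 under day 28", and that column has no PCR either.

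**Definition.** The protocol's efficacy assessments, under PCR nasopharyngeal swab, state: "If a subject with a previous positive PCR result obtains two negative PCR results consecutively, they are considered clear of active infection". The SAP does not refer to this rule.

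**Population.** The inclusion criteria require suspected infection, not a positive test. SAP section 4 defines the efficacy set by receipt of all four infusions, and SAP 7.2.3 applies it to the secondary endpoints.

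**Model.** SAP 7.1.4.1 names survival and Cox models for time-to-event outcomes in general. SAP 7.2.4.2 lists the secondary endpoints modelled through Visits 5 and 6 but does not mention PCR. SAP 7.2.2 promises means for every endpoint.

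**The concern.** A time-to-event analysis needs a defined event, a set of patients who can have it, and a period in which it can be observed. Here the stated period runs well past the last planned measurement, the set includes patients for whom clearance has no meaning, and the event could be one negative or two.

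Two analysts could follow this SAP and report different event counts, risk sets and follow-up times. The protocol's efficacy analysis section would read a shorter time in the treated arm as a shorter contagious period. That conclusion would rest in part on patients who may never have been infected, and on a window with no scheduled test in its later part.

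**Working it through.** The documents give no event rate, clearance time or power for this endpoint, so there is no figure to reproduce.

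**Step 1: unobserved time.** The last scheduled swab is on Day 10, so 28 − 10 = 18 days follow it, and 18/28 = 64%. With the ±3-day window (protocol, Assessments by Week) the last swab can fall as late as Day 13, so 28 − 13 = 15 days and 15/28 = 54%.

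**Step 2: which swab patterns give an event.** Take swabs on Days 0, 3, 7 and 10 (P positive, N negative) and the protocol's rule: an earlier positive, then two negatives in a row. Three later swabs give 2³ = 8 patterns for each starting state.

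| Starting state | Patterns with an event | Which, and first negative of the pair |
|---|---|---|
| Positive on Day 0 | 3 of 8 | PNNN, PNNP (Day 3); PPNN (Day 7) |
| Negative on Day 0, no earlier positive | 1 of 8 | NPNN (Day 7) |
| Negative on Day 0, earlier documented positive | 5 of 8 | NNNN, NNNP, NNPN, NNPP (Day 0); NPNN (Day 7) |

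These are counts of patterns, not probabilities.

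- A patient positive on Day 0 can start a confirmed clearance only at the Day 3 or Day 7 swab. The pattern PPPN has no scheduled swab to confirm it.
- A patient negative throughout, with no earlier positive, has no event. If a single negative were the event, the same patient would have it on Day 0, at time zero.

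**Step 3: illustration of what the schedule can capture.** Assume, for patients positive on Day 0, exponential clearance with median m days, an error-free test, no return to positive, and swabs on nominal days. Then F(t) = 1 − 2^(−t/m). The share of clearances by Day 28 that the schedule can register is F(7)/F(28) under the two-negative rule and F(10)/F(28) under a single negative. For m = 14, F(7) = 0.29, F(10) = 0.39 and F(28) = 0.75, which gives 39% and 52%. The documents give no median, so a range is shown.

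| Assumed median (days) | Two negatives | One negative |
|---|---|---|
| 5 | 63% | 77% |
| 7 | 53% | 67% |
| 10 | 45% | 58% |
| 14 | 39% | 52% |
| 21 | 34% | 47% |

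**The case against.** The best defence is that the Day 28 horizon comes only from a list heading. That heading speaks of change from baseline, which does not suit a time-to-event endpoint anyway. SAP 7.2.4.2 does not place PCR among the Visit 6 models, and the survival models in SAP 7.1.4.1 would ordinarily censor a patient at the last observation. This has force. A reader might infer that the plan will report a Day 28 proportion not cleared, counting untested patients as positive. No section plans that. But the SAP never states the censoring point, and its only stated horizon is Day 28.

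A reader might also infer that every patient negative on Day 0 is without an event. The protocol's rule asks for a previous positive, not a Day 0 positive. It allows a confirmatory test to be in progress at screening, and COVID-19 test results go into the medical history. An earlier positive, or conversion on Day 3 followed by two negatives, makes an event possible. Only patients who never test positive are excluded by definition.

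Nor do the documents show that nothing after Day 10 could be known. Table 2 marks a medical history review at Day 28, so an outside result might be recorded. What they support is that no swab is scheduled.

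Finally, a reader might equate the dilution of the treatment effect with the share of uninfected patients. The documents give no such share, and the equality is not shown for a hazard ratio.

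**Conclusion.** The point stands in this form. The stated horizon exceeds the swab schedule by 18 days nominally (15 at the latest swab), and the analysis set includes patients who may never test positive. Such patients have either no possible event or one at time zero. Under the two-negative rule, a patient positive on Day 0 has only two swabs at which a confirmed clearance can start.

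This goes beyond missing detail, because applying the horizon and population as written would give an ill-defined risk set. It is not evidence of bias in favour of either arm. The schedule figures rest on Table 2 and its window. The two-swab limit also assumes that the protocol's rule defines the endpoint, which the SAP leaves open. The percentages in Step 3 rest on assumed medians and are illustrative.

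A separate matter also needs reconciling. The endpoints part of the protocol's statistical section lists time to clearing PCR as primary, while its study endpoints section and the SAP list it as secondary. The finding here does not depend on that.

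**What to change.** In the SAP:

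1. Move the endpoint to the list that runs through Visit 5 (Day 10).
2. Restrict the analysis to patients with a documented positive PCR at Day 0 or earlier, with the acceptable source and look-back period prespecified. If the Day 0 swab precedes the first infusion, this is a baseline restriction.
3. Define the event as the first of two consecutive negatives, as in the protocol. Say how to treat a patient with an earlier positive who is negative on Days 0 and 3, because that event would be dated at time zero.
4. Censor at the last swab at which the event could still be observed. With scheduled swabs only, that is the Visit 4 (Day 7) swab. Censoring a lone Day 10 negative at Day 7 and a Day 10 positive at Day 10 would let the result decide the censoring.
5. Use a discrete-time or interval-censored survival model, since clearance is known only to lie between visits. Name it in SAP 7.2.4.2, and replace the means promised in SAP 7.2.2 with a time-to-event summary.

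The cost is SAP wording and fewer patients in this endpoint, including any who first test positive after Day 0. No new data are needed, and the SAP is still marked as a draft.
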